10.1. Subject Completion

A subject will be considered as having completed the study, regardless of whether the subject is on or off study drug, if the subject is followed until a time point between the notification of the GTED and the GTED (eg, subjects who complete the treatment need to have a final posttreatment follow-up visit; subjects who withdraw early from the treatment need to have a final contact after the notification of the GTED), or at the time of death for subjects who die prior to the GTED. The occurrence of a nonfatal MI, nonfatal stroke or any other safety or efficacy outcome does not comprise study completion and is not a criterion for withdrawal from the study or study drug.

10.2. Premature Discontinuation of Study Medication

A subject will discontinue study medication for any of the following reasons:

- The investigator believes that for safety or tolerability reasons it is essential for the subject to stop treatment
- The investigator formally unblinds the subject's treatment allocation
- The subject becomes pregnant (study therapy should be immediately discontinued based upon a positive urinary hCG, and permanently discontinued if confirmed by a serum β -hCG test)
- The subject's eGFR is <15 mL/min/1.73m² (as reported by the central laboratory).

Note: the central laboratory will alert the investigator for eGFR falls to <15 mL/min/1.73m². A repeat determination should be performed within 2 weeks, and study treatment discontinued if the repeat eGFR is <15 mL/min/1.73m² (unless a reversible cause is identified [eg, short-term illness or transient volume depletion] in which case an additional repeat determination can be performed after resolution of the short-term illness).

- Subject requires dialysis or renal transplantation
- Subject requires disallowed therapy (refer to Section 8, Prestudy and Concomitant Therapy)
- The subject experiences a serious adverse event of biochemically-confirmed (eg, pH, serum ketones, anion gap) DKA.

Premature discontinuation of study treatment does not comprise study completion and is not a criterion for withdrawal from the study. All subjects who prematurely discontinue study treatment should continue study follow-up, although the nature of follow-up may be modified (see Section 9.1.4 and the Time and Events Schedule). Treatment should be recommenced wherever possible and routinely considered at every visit following discontinuation.

Subjects who decide to withdraw from double-blind study drug must be interviewed by the investigator so as to determine if a specific reason for withdrawal can be identified. Withdrawing

subjects should be explicitly asked about the contribution of possible adverse events to their decision to withdraw consent, and any adverse event information elicited should be documented. If the subject elects to withdraw due to an adverse event, the event should be recorded as the reason for withdrawal, even if the investigator's assessment is that the adverse event would not require study drug withdrawal. The reason for withdrawal is to be documented in the eCRF and in the source documentation. Study drug assigned to the withdrawn subject may not be assigned to another subject. Subjects who withdraw will not be replaced.

10.3. Reinstitution of Treatment for Subjects Who Have Prematurely Discontinued Double-Blind Study Drug to Active Status

Subjects for whom study drug is interrupted as a result of an adverse event, a life event (eg, temporary relocation to care for an ill family member), or other unforeseen circumstance should be encouraged to recommence study drug unless there is a clear contraindication at the discretion of the investigator, with concurrence from the sponsor's medical monitor.

Study drug interruptions, occurring for any reason and lasting 7 days or longer, will be documented on the eCRF.

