4.3. Exclusion Criteria

Potential subjects who meet any of the following criteria will be excluded from participating in the study:

Diabetes-Related/Metabolic

- History of diabetic ketoacidosis, T1DM, pancreas or beta-cell transplantation, or diabetes secondary to pancreatitis or pancreatectomy
- History of one or more severe hypoglycemic episodes within 6 months before screening
Note: a severe hypoglycemic episode is defined as an event that requires the help of another person.
- History of hereditary glucose-galactose malabsorption or primary renal glucosuria
- Ongoing, inadequately controlled thyroid disorder
Note: subjects on thyroid hormone replacement therapy must be on a stable dose for at least 6 weeks before Day 1.

Renal/Cardiovascular

- Renal disease that required treatment with immunosuppressive therapy or a history of chronic dialysis or renal transplant. Note: subjects with a history of treated childhood renal disease, without sequelae, may participate.
- Myocardial infarction, unstable angina, revascularization procedure, or cerebrovascular accident within 3 months before screening, or a planned revascularization procedure, or history of New York Heart Association (NYHA) Class IV cardiac disease ([The Criteria Committee of the New York Heart Association](#)).
- Known ECG findings within 3 months before screening that would require urgent diagnostic evaluation or intervention (eg, new clinically important arrhythmia or conduction disturbance)

Gastrointestinal

- Known history of hepatitis B surface antigen or hepatitis C antibody positive (unless known to be associated with documented persistently stable/normal range aspartate aminotransferase [AST] and alanine aminotransferase [ALT] levels), or other clinically active liver disease
- Any history of or planned bariatric surgery

Laboratory

- eGFR <30 mL/min/1.73m² at screening visit
- ALT levels >2.0 times the upper limit of normal (ULN) or total bilirubin >1.5 times the ULN, unless in the opinion of the investigator and as agreed upon by the sponsor's medical officer, the findings are consistent with Gilbert's disease

Other conditions

- History of malignancy within 5 years before screening (exceptions: squamous and basal cell carcinomas of the skin and carcinoma of the cervix in situ, or a malignancy that in the opinion of the investigator, with concurrence with the sponsor's medical monitor, is considered cured with minimal risk of recurrence)

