Study drug may be interrupted (eg, for safety and/or tolerability reasons such as hospitalizations for major surgical procedure or serious medical illness). Study drug interruptions, occurring for any reason and lasting 7 days or longer, will be documented on the eCRF. Study drug should be reinstated once the subject has recovered and the safety and/or tolerability concern is no longer present.

For subjects who develop conditions that are associated with or leading to amputation such as a lower extremity infection, skin ulcer, osteomyelitis, gangrene or critical limb ischemia, study drug should be interrupted until the condition has resolved in the opinion of the investigator. In the event of an amputation, restarting of dosing with canagliflozin should only be done after careful consideration of the individual risk:benefit and following discussion with the sponsor.

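### Protocol 10.2 orders study drug to stop for serious confirmed DKA and formal unblinding, then urges restart with no exception, and 10.3 does not clearly govern such restarts

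*Protocol*

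**What the plan says.** Protocol Section 10.2 opens its list in mandatory terms: "A subject will discontinue study medication for any of the following reasons". Seven reasons follow. Two matter most here: "The investigator formally unblinds the subject's treatment allocation" and "The subject experiences a serious adverse event of biochemically-confirmed (eg, pH, serum ketones, anion gap) DKA". The amendment history shows that INT-3 added the DKA item. One item, pregnancy, carries a statement of permanence: "study therapy should be immediately discontinued based upon a positive urinary hCG, and permanently discontinued if confirmed by a serum" test.

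The paragraph after the list says that stopping treatment is not withdrawal from the study and that follow-up continues. It closes with "Treatment should be recommenced wherever possible and routinely considered at every visit following discontinuation". No listed reason is carved out.

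Section 10.3 is headed as covering subjects who have prematurely *discontinued* double-blind drug. Its body addresses subjects whose drug is *interrupted* by an adverse event, a life event or another unforeseen circumstance. They "should be encouraged to recommence study drug unless there is a clear contraindication at the discretion of the investigator", with the concurrence of the sponsor's medical monitor.

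Section 6.1 has a general sentence on interruptions: drug is reinstated after recovery, once the safety or tolerability concern has gone. No sponsor concurrence is mentioned. After an amputation, restart "should only be done after careful consideration of the individual risk:benefit and following discussion with the sponsor".

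SAP Section 2.3.2 defines the last dose date as the date the last double-blind dose was taken, and equates it with permanent discontinuation whatever temporary interruptions occurred.

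**The concern.** A mandatory stop and a general instruction to restart stand in the same section, and nothing says which stops the instruction covers. A site with a subject who has had serious confirmed DKA is told to stop the drug, then told to look for a chance to recommence at every later visit. Whether a contraindication check and medical-monitor concurrence come first depends on whether 10.3 is read by its heading or by its body.

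Two sites could therefore treat the same event differently while both following the protocol. At stake are consistent handling of subjects after a safety stop and, for unblinded subjects, whether treatment could resume with the allocation known in a double-blind trial. There is also a smaller analysis issue, because exposure and On-Treatment time depend on a line between permanent and temporary stops that the protocol does not draw.

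**Working it through.** No figure in the plan needs reproducing. The check is a comparison of texts, then a short calculation of the exposure effect.

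**Step 1. The seven reasons in Protocol 10.2 against the restart sentence.**

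| Reason | Marked permanent? | Is restart settled elsewhere? |
|---|---|---|
| Investigator's safety or tolerability judgement | No | Only if 6.1 and 10.3 apply to stops |
| Formal unblinding | No | No |
| Pregnancy | Yes, once serum-confirmed | Yes: 12.2.3 and Time and Events footnote i |
| eGFR below 15 | No | Partly: repeat test before stopping; a value still below 15 still meets the criterion |
| Dialysis or transplantation | No | Partly: a continuing need still meets the criterion |
| Disallowed therapy | No | Partly: a continuing need still meets the criterion |
| Serious confirmed DKA | No | No |

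DKA is a past event that resolves, so neither the stop criterion nor any other sentence settles what happens afterwards. Unblinding cannot be undone, which argues against restart, but no sentence says so.

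**Step 2. Do the neighbouring sections fill the gap?**

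- 10.3 would supply two limits, but heading and body name different groups. Its grammar also leaves open whether the medical monitor concurs with the restart or with the judgement of contraindication.
- The general sentence in 6.1 is about interruptions. It gives hospitalization for serious medical illness as an example, which a DKA admission could also fit on its face. It states a recovery condition and no concurrence.
- The boundary between an interruption and a discontinuation is not defined in 6.1, 10.2 or 10.3.

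**Step 3. Effect on exposure and the On-Treatment window.**

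Let a subject stop after the dose on day *s*, restart on day *r*, and take the final dose on day *d*.

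- Exposure by SAP 3.4 (Day 1 to last dose date, inclusive) = *d* days.
- Days on drug = *s* + (*d* − *r* + 1).
- Off-drug days counted as exposure = *d* − *s* − (*d* − *r* + 1) = *r* − *s* − 1.
- SAP Table 1 extends the On-Treatment window 30 days past the last dose for adverse events. Without a restart the window would already cover 30 off-drug days, so the restart adds max(0, *r* − *s* − 31) off-drug days to it.

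The post-treatment schedule gives natural values for *r*, since restart is to be considered at visits:

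- Restart at the 30-day visit (*r* = *s* + 30): 29 off-drug days counted as exposure, 0 added to the adverse event window.
- Restart at the first 26-week visit (*r* = *s* + 26 × 7 = *s* + 182): 181 off-drug days counted as exposure, 182 − 31 = 151 added to the adverse event window. For laboratory values other than ACR, where the extension is 2 days, 182 − 3 = 179 are added.

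These are per-subject illustrations. The documents do not say how many subjects restart or when.

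**The case against.** The strongest reply is that the sections should be read together. The restart sentence is qualified by feasibility and asks only that restart be considered; a sensible investigator would not treat it as an order after DKA. The next section, by its heading, covers discontinued subjects and adds a contraindication limit and medical-monitor concurrence. DKA-related events must reach the sponsor within 24 hours, suspected DKA is adjudicated, and the IDMC reviews unblinded safety data (Protocol 9.3.4 and 9.4).

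Part of this stands. The text permits inconsistent restarts; it does not compel them, and there is oversight. But reporting and adjudication tell the sponsor that an event occurred without giving the site a restart rule, and the protection in 10.3 rests on a heading that its own body does not match.

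The objection also disposes of several stronger readings that a reader might be tempted by:

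- *Pregnancy is another open case.* It is not: serum-confirmed pregnancy is a permanent stop in 10.2 and is barred again in 12.2.3 and footnote i.
- *Dialysis is an equally clear case.* A continuing need still meets the stop criterion.
- *The restart sentence conflicts with entry rules*, because "History of diabetic ketoacidosis, T1DM, pancreas or beta-cell transplantation" excludes a subject. Entry criteria govern enrolment. The protocol openly applies other rules after randomization: eGFR below 30 excludes at screening, while the stop is at below 15.
- *The amputation text in 6.1 is a third competing condition.* It is a specific rule for an event that is not on the 10.2 list.
- *Restarts would distort the adjudicated DKA results.* The main DKA analysis uses the On-Study set regardless of last dose, and its rate counts subjects with an event, so a subject who stopped for adjudicated DKA is already counted (SAP 5.2.2 and 5.2.2.8).
- *The programme's acidosis counts in Protocol 1.1.2 size the problem.* They cover wider terms than confirmed DKA and say nothing about restarts.

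**Conclusion.** The point holds in a limited form. Section 10.2 sets a mandatory stop and then directs sites toward restart without excepting any reason. For serious confirmed DKA, and next for formal unblinding, no other sentence clearly says whether or on what terms restart may occur. This is a stated rule that needs reconciling, not merely an omitted detail, and it bears on subject safety.

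Its size in subjects is unknown, because no restart frequency is given. The analysis effect is secondary: it falls on exposure and On-Treatment summaries, and SAP 2.3.2 and 3.4 already disregard interruptions by design. The primary and secondary efficacy analyses use the ITT set, whose data period does not depend on the last dose date.

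The conclusion rests on two readings: that the closing sentence of 10.2 covers every listed reason, since none is excepted, and that a restarter's last dose date is the final dose after restart, as the opening words of the SAP definition indicate.

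**What to change.** Reconcile Protocol 10.2, 10.3 and the general reinstatement sentence in 6.1:

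- For each reason listed in 10.2, state whether the recommencement sentence applies.
- State whether the conditions in 10.3 govern discontinued as well as interrupted subjects, and align its heading and body.
- Leave the amputation text in 6.1 as its own rule. Nothing here calls for a single approval route across the sections.

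Which rule applies to which reason is for the sponsor and the safety committees; this point takes no position on it.

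The cost is amendment wording and a communication to sites, with no new data or procedures. If the sponsor narrows the restart sentence, there may be slightly fewer restarts.

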10.4. Lost to Follow-up

If a subject is lost to follow-up, all possible efforts must be made by the study site personnel to contact the subject and to achieve as complete follow-up as possible until after the site notification of the GTED. The measures taken to achieve follow-up are discussed in Section 10.5, Circumstances for Reduced Follow-up, and must be documented. The informed consent form will stipulate that even if double-blind study drug is discontinued, he/she will agree to continue follow-up.

10.5. Circumstances for Reduced Follow-up

There may be circumstances in which a reduced follow-up schedule is required and the options for this are described in Section 9.1.6, Post-Randomization Follow-up for Participants Unable to Attend Scheduled Visits. If one of these regimens is not possible, it will be necessary for the site investigator to contact the Sponsor representative to indicate the reasons why no further follow-up is necessary. It is important to note that a subject declining further follow-up does not constitute withdrawal of consent and the alternate follow-up mechanisms that the participant agreed to when signing the consent form will still apply (eg, searches of databases, use of locator agencies at study completion) as permitted by local regulations.

In this regard, the subject will be asked as a condition of entry into the study to agree to grant permission for the investigator to consult family members, the subject's physicians and medical records, or public records, including the use of locator agencies as permitted by local law, to determine the subject's status with respect to the CV safety composite endpoint, in the event the subject is not reachable by conventional means (eg, office visit, telephone, e-mail, or certified mail). The subject is also to be advised that if the site of the study doctor closes, and the study doctor cannot reach the subject to inform him/her, the contact information will be transferred to another site where a new study doctor will consult with family members, the subject's physicians

and medical records, or public records, including the use of locator agencies as permitted by local law, to determine the subject's endpoint status.

10.6. Withdrawal of Consent

Withdrawal of consent should be a very unusual occurrence in a clinical trial. The investigator should make every effort to maintain a good relationship with subjects to avoid this occurrence. In many instances where withdrawal of consent could potentially be recorded, the subject could be expected to be followed-up through one of the alternative follow-up mechanisms discussed in Section 10.5, Circumstances for Reduced Follow-up.

Withdrawal of consent in this trial may only be logged in the eCRF after a discussion between the investigator and the appropriate sponsor representative.

For subjects truly requesting withdrawal of consent, it is recommended that the subject withdraw consent in writing; if the subject or the subject's representative refuses or is physically unavailable, the site should document and sign the reason for the subject's failure to withdraw consent in writing.

If a subject had previously withdrawn consent but decides to retract that withdrawal, the subject will be reconsented. The investigator will be responsible for making all required notifications to the IRB or Ethical Committee.

11. STATISTICAL METHODS

11.1. Analysis Sets

The intent-to-treat (ITT) analysis set includes all subjects who are randomized via the Interactive Web Response System (IWRS). The assessment of the primary and most of the secondary objectives will be based upon this analysis set.

The modified intent-to-treat (mITT) or On-Treatment analysis set includes all subjects who are randomly assigned to a treatment group and receive at least one dose of double-blind study. It will be used in the analyses assessing on-treatment effects, e.g. time slope of on-treatment eGFR.

Efficacy data will be analyzed according to the initial randomization assignment regardless of actual treatment received.

11.2. Sample Size Determination

Based on the interim data from the CANVAS study, where ACR was measured periodically at scheduled visits, it is projected that the annual progression rate for the CANVAS-R study will be approximately 7.4%. Assuming a 22% relative risk reduction for albuminuria progression, an annual progression rate in the placebo arm of 7.4%, an 18-month accrual period, a maximum treatment period of 36 months, and an annual discontinuation (from treatment) rate of 10%, it is estimated that 693 events will be reported. With 5,700 subjects enrolled, the power to demonstrate the superiority of canagliflozin over placebo for albuminuria progression is 90.5%, with type I error rate of 0.05 (two-sided).

11.3. Efficacy Analyses

11.3.1. Primary Efficacy Analysis

In this study, duplicate urine specimens will be collected for all ACR measurements. At each visit, the geometric mean of the duplicate measurements will be computed and used for all subsequent analysis unless otherwise specified.

Subjects will be classified as having normoalbuminuria (urinary ACR of <3.5 mg/mmol [<30 mg/g]), microalbuminuria (ACR ≥ 3.5 mg/mmol [≥ 30 mg/g] and ≤ 35 mg/mmol [≤ 300 mg/g]), or macroalbuminuria (ACR of >35 mg/mmol [>300 mg/g]).

The primary efficacy analysis seeks to demonstrate the superiority of canagliflozin in the reduction of albuminuria progression relative to placebo.

The time from first study drug administration to first visit date observing progression (ie, not using the visit date of the repeat sample collection) of albuminuria will be analyzed using a Cox proportional hazards regression model. The model will include treatment and baseline albuminuria status as covariates. The hazard ratio between canagliflozin and placebo will be provided, including its 95% confidence interval. The observation period for this time-to-event analysis will include all available measurements from first study drug administration to the visit date of the last ACR measurement. Subjects with no progression will be censored at the visit date of the last albuminuria measurement.

As a sensitivity analysis, the actual onset time of progression of albuminuria can be determined to lie within an interval from a sequence of examination times (ie, data are interval censored). As a supportive analysis, the accelerated failure time (AFT) model with log normal error structure will be implemented considering interval censoring. The dependent variable in AFT model is logarithm of time to progression of albuminuria. The model will include treatment group and baseline albuminuria status as covariates. We can use speed of progression to interpret AFT model. For any time (t), the probability of a subject on placebo progression-free beyond time t is the probability of a subject on canagliflozin progression-free beyond t/α , where α is the acceleration factor which can be estimated from the model. Additional sensitivity analyses will be specified in the study SAP.

The cumulative progression rate derived from Kaplan-Meier estimate will be displayed graphically to evaluate the timing of progression and the consistency of the treatment effect over time.

